# 8.2.3 Sensitivity analysis: Matching-adjusted indirect comparison, external studies in turn

For each external study separately, a matching-adjusted indirect comparison (MAIC) will be used to compare the control group in that study with the treatment group in the DCVax®-L trial. The MAIC technique is explained in detail in Appendix D.

The MAICs will be adjusted for the following characteristics.

Table 7: Characteristics to be matched via MAIC: selected studies, recurrent GBM

Study	MGMT	KPS	Age	Sex	Race
Brandes 2018	✓	✓	✓	✓	
Wick 2017	$\checkmark$		✓	$\checkmark$	
Wick 2010		$\checkmark$	$\checkmark$	✓	
Brandes 2016			$\checkmark$	✓	✓
Lombardi 2019	$\checkmark$		$\checkmark$	$\checkmark$	
Taal 2014	$\checkmark$		$\checkmark$	✓	
Narita 2019		$\checkmark$	$\checkmark$	✓	
Cloughesy 2017	✓	$\checkmark$	✓	✓	✓

Study	MGMT	KPS	Age	Sex	Race
Galanis 2019			√	✓	_
Lee 2020		$\checkmark$	✓	✓	$\checkmark$

The hazard ratio and a 95% confidence interval as well as a 2-sided p value will be reported. Estimates of survival probability at 6, 12, 18, 24, 30, 36, 42, 48, 54 and 60 months will be calculated (with 95% confidence intervals).

#### 8.2.4 Secondary analyses

Secondary analyses will repeat the analyses above for the following populations:

- Patients who were originally assigned to DCVax®-L, and who received DCVax®-L under the crossover option following progression. This comparison investigates whether 'priming' with DCVax®-L may result in a benefit;
- All patients, irrespective of original treatment assignment, who received DCVax®-L under the
  crossover option following progression. This comparison investigates the impact of DCVax®L on survival for patients who experience disease recurrence, irrespective of their treatment
  prior to recurrence.

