#### 1.1 Study design

The 020221 clinical trial was designed as a randomized, placebo-controlled, double blinded, multicenter, multi-national Phase III trial (the "Trial"). Subjects with newly diagnosed GBM (confirmed through independent central pathology review) having surgically accessible, unilateral tumor for which surgical resection is indicated, with intent to perform a gross total or near gross total resection, were eligible to be considered for enrolment.

Following standard of care therapy, consisting of surgical resection followed by external beam radiation and concurrent chemotherapy (temozolomide), subjects not showing signs of early recurrence are randomized to either DCVax®-L or Placebo with a randomization ratio of 2:1. Subjects are stratified for randomization by site and by MGMT methylation status (methylated or not methylated).

All subjects in the Trial are followed for the collection of data on progression and survival.

A crossover option was included in the Trial design on demand of patients and investigators, and was necessary to enable recruitment and retention of patients when the Trial began 13 years ago in 2007. The crossover option in this Trial is different from various other crossover designs sometimes used in other trials. In this Trial, all subjects -- from both arms of the Trial -- who have tumor progression (recurrence) have the option to receive DCVax®-L treatment post-progression. In addition, all subjects who do receive DCVax®-L after progression receive it on the same basis (same treatment schedule, etc.), regardless of which treatment arm of the Trial those patients were in before progression. Of crucial importance: under this design, all parties remain blinded as to which treatment the subjects received before progression (the patients, investigators and sponsor all remain blinded).

The large number of patients who elected to cross over depleted the control arm in the Trial. About 90% of all patients in the ITT population crossed over, including most of the patients in the original control arm. This depletion of the control arm left too few patients for effective comparisons within the Trial.

In addition, even if comparisons within the Trial were still feasible, they could lead to misleading results. In patients who were originally assigned to the control arm and who receive DCVax®-L only

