#### 8.2 Analysis for OS in recurrent GBM: comparison with external study control groups

This endpoint, will apply to those subjects who were originally assigned to the placebo arm and who received standard of care + placebo until disease progression, and who then crossed over to receive DCVax®-L post-progression. The survival of these subjects will be analyzed via comparison to external studies in recurrent GBM.

Secondary analyses will evaluate the same endpoint of OS post progression for the following populations:

<sup>10 For this study population: Class III: Age < 50 and KPS ≥ 90. Class IV: Age < 50 and KPS < 90, or Age ≥ 50.

- Patients who were originally assigned to DCVax®-L, and who received DCVax®-L under the crossover option following progression
- All patients, irrespective of original treatment assignment, who received DCVax®-L under the crossover option following progression

A systematic literature review for recurrent GBM studies has been conducted by independent experts to identify appropriate studies in recurrent GBM from which survival data for control groups could be obtained, in the same manner as the independent expert selection of the appropriate external studies for newly diagnosed GBM. The control patients from ten studies shown in Table 6 [5, 19-27], which were conducted in similar populations as in the current Phase III study, in trials which each had a control arm will be included. The control patients were treated with physician's choice of therapy or best available standard treatment, which could include standard treatments like lomustine or bevacizumab.

Table 6: Studies selected providing comparable control arms: recurrent GBM

Lead	Year	Journal	CONTROL GROUP		OS Kaplan-Meier curves	
author			Treatment arm	N	Median OS (months)	available for subgroups of interest
Brandes	2018	The Oncologist	Lomustine plus placebo	62	5.5	None
Wick	2017	NEJM	Lomustine	149	8.6	None
Wick	2010	JCO	Lomustine	92	7.1	None
Brandes	2016	Neuro- Oncology	Lomustine plus placebo	40	7.5	None
Lombardi	2019	Lancet Oncology	Lomustine	60	5.6	None
Taal	2014	Lancet Oncology	Best supportive care	30	8.0	None
Narita	2017	Neuro- Oncology	Lomustine	46	8.0	None
Cloughesy	2017	JCO	Bevacizumab plus placebo	65	12.6	MGMT methylated (N = 26), unmethylated (N = 25)
Galanis	2019	Cancer	Bevacizumab plus placebo	38	7.7	None
Lee	2020	Cancer	Bevacizumab plus placebo	58	11.5	None

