#### 8.2.1 Primary analysis: simple proportional hazards model

The primary analysis will be a comparison between the reconstructed individual patient data for all subjects, pooled across the external studies, with the subjects who crossed over from the placebo arm and were treated with DCVax®-L post-progression. Cox's proportional hazards model will be used.

Median survival and a 95% confidence interval will be reported.

The hazard ratio (HR) and a 95% confidence interval will be reported, as well as the associated 2-sided p value. Estimates of survival probability at 6, 12, 18, 24, 30, 36, 42, 48, 54 and 60 months will be calculated (with 95% confidence intervals).

Kaplan-Meier estimates of the survival functions for the DCVax®-L population and the comparator population will be plotted.

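### SAP 8.2.4 presents a comparison with external controls as a study of DCVax-L priming, but a favourable hazard ratio there cannot be attributed to priming

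*Combined protocol and SAP*

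**What the plan says.** Secondary Endpoint #1 is overall survival after progression in placebo-arm patients who crossed over to DCVax-L. SAP section 8.2 sets the comparator: "The survival of these subjects will be analyzed via comparison to external studies in recurrent GBM". Section 8.2.1 fits a Cox model to reconstructed external patient data, "pooled across the external studies, with the subjects who crossed over from the placebo arm and were treated with DCVax®-L post-progression". Section 8.2.2 repeats this by MGMT status. For each external study, section 8.2.3 uses a matching-adjusted indirect comparison to "compare the control group in that study with the treatment group in the DCVax®-L trial". Section 3.1.1 names the same external comparator for the endpoint.

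Section 8.2.4 then states: "Secondary analyses will repeat the analyses above for the following populations". The first population is "Patients who were originally assigned to DCVax®-L, and who received DCVax®-L under the crossover option following progression", and the purpose given for it is: "This comparison investigates whether 'priming' with DCVax®-L may result in a benefit".

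On the vaccine given at crossover, section 1.1 says that patients from both arms "receive it on the same basis (same treatment schedule, etc.), regardless of which treatment arm of the Trial those patients were in before progression".

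Neither the SAP nor the protocol plans a comparison of post-progression survival between crossover patients from the two arms, a ratio of their two external hazard ratios, or an interaction test.

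**The concern.** Priming here means DCVax-L given before progression, over and above DCVax-L given after it. The patients analysed had both; the external controls had neither and come from other trials. One hazard ratio cannot separate these three differences. The matching-adjusted comparison does not help, because Table 7 lists at most MGMT, KPS, age, sex and race, and not treatment received before progression.

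The SAP itself treats a post-progression benefit as a live possibility: section 1.1 discusses it and Secondary Endpoint #1 tests it. If that endpoint succeeds, a favourable result in 8.2.4 is to be expected with no priming effect at all. Because the interpretation is written into the plan, such a result would be reported as evidence on priming with the authority of pre-specification. Conversely, a real priming effect could be hidden if the external patients had a better prognosis.

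**Working it through.** The plan gives no figure for this analysis, so there is none to reproduce. As a check on the formula, the SAP's own OS inputs (section 1.3.2: 233 events, medians 17 and 25.3 months, one-sided 0.025, 2:1 allocation) give Φ(|ln(17/25.3)| × √(233 × 2/9) − 1.96) = Φ(0.398 × 7.196 − 1.96) = 0.816, against the stated 80.5%.

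**What the hazard ratio contains.**

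HR(primed vs external) = HR(post-progression DCVax-L) × HR(priming) × between-trial difference

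HR(unprimed vs external) = HR(post-progression DCVax-L) × between-trial difference

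Only the ratio of the two lines bears on priming, and the plan does not form it. Even that ratio equals HR(priming) only if the two crossover groups are otherwise alike.

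**Inputs.**
- External controls (Table 6): 62+149+92+40+60+30+46+65+38+58 = 640.
- ITT 331 and DCVax-L arm 232 (sections 1 and 1.2.1), so placebo 331 − 232 = 99.
- Crossover: section 1.1 says about 90% of the ITT population crossed over, 0.90 × 331 = 298. That allows 298 − 232 = 66 to 99 placebo-arm and 298 − 99 = 199 to 232 DCVax-L-arm crossovers. Section 1.2.3 instead says 90% received DCVax-L. If the whole DCVax-L arm is counted in that, it again gives 66 placebo crossovers, but it leaves the DCVax-L-arm crossover count open.
- Assumed, not in the documents: primed n from 150 to 232; 80% to 95% deaths; proportional hazards; priming HR exactly 1; no between-trial difference.

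**Chance of nominal significance with no priming effect.** Section 8.2.1 reports a 95% interval and a two-sided p value, so 2.5% in the direction of benefit is used:

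P = Φ(|ln HR| × √(d·p·(1−p)) − 1.96), with d = f × (n + 640) and p = n/(n + 640).

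Example, n = 150, f = 0.80, HR 0.80: d = 632, p = 0.190, √(d·p·(1−p)) = 9.86, so Φ(0.223 × 9.86 − 1.96) = Φ(0.24) = 0.60.

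| Primed n | HR 0.90 (80% / 95% deaths) | HR 0.80 | HR 0.70 |
|---|---|---|---|
| 150 | 0.18 / 0.20 | 0.60 / 0.67 | 0.94 / 0.97 |
| 199 | 0.21 / 0.24 | 0.69 / 0.76 | 0.98 / 0.99 |
| 209 | 0.22 / 0.25 | 0.71 / 0.78 | 0.98 / 0.99 |
| 232 | 0.23 / 0.27 | 0.74 / 0.81 | 0.99 / >0.99 |

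HR here is the assumed post-progression DCVax-L effect. At HR 1.0 the chance is 0.025. A Cox simulation (209 primed, 640 external, external median 8 months, 300 runs per setting) gave 0.27, 0.81 and 0.997 at HR 0.90, 0.80 and 0.70.

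**The internal comparison.** With no priming effect and otherwise similar groups, it rejects at its nominal rate (0.017 to 0.027 in the same simulation, with 66 unprimed). Its precision is SE = √(1/(f·n₁) + 1/(f·n₀)). With 199 and 99 patients and 95% deaths, SE = 0.126 and the 95% factor is exp(1.96 × 0.126) = 1.28. With 232 and 66 and 80% deaths, SE = 0.156 and the factor is 1.36. With 150 and 66 and 80% deaths it would be 1.38. With 150 to 209 primed, 66 to 89 unprimed and 90% deaths, power is about 0.91 to 0.97 for a priming HR of 0.6, 0.63 to 0.76 for 0.7, and 0.30 to 0.39 for 0.8.

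**The case against.** The analysis is not confirmatory. Table 2 lists only the placebo crossover cohort for this endpoint, and the gatekeeping in section 8.3.1 follows Table 2, so no alpha attaches to the DCVax-L-arm crossover patients. The SAP's wording is also tentative. A reader might infer that the probabilities above are rates of false priming claims. They are not, because the plan attaches no decision rule to this analysis. They show how often the result would look favourable for a reason other than priming. This part of the objection stands and limits the severity.

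A reader might also infer that the trial cannot address priming at all. That goes too far. Both crossover groups are compared with the same external pool by the same method, so the comparator roughly cancels when the results are set side by side. Secondary Endpoint #4 is a randomised OS comparison in which most placebo patients later received DCVax-L, so it bears on adding earlier treatment, although it runs from randomisation and is a different estimand. What is missing is a direct contrast with an interval.

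It is equally tempting to say that placebo-arm crossover patients isolate priming. The SAP does not support this. Section 1.2.3 says vaccine-induced pseudo-progression is frequent and is counted as progression, and section 8.3.2 expects early events to misrepresent progression differently in the two arms. Some primed patients would then start the post-progression clock too early and appear to survive longer. Protocol section 8.4 adds that DCVax-L-arm patients may have exhausted their supply. The external comparison shares these problems and adds two further differences.

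**Conclusion.** The stated purpose does not match the analysis. A favourable hazard ratio in 8.2.4 would be evidence about DCVax-L before and after progression together, subject to between-trial differences, and could not be credited to priming. With no priming effect and a post-progression HR of 0.80, nominal significance would occur with probability of about 0.6 to 0.8. This rests on assumed crossover counts and event fractions, since the documents give no counts by arm and their two 90% statements differ.

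A reader might carry over the SAP's 17/25.3 = 0.67 and conclude that a favourable result is almost certain. That ratio is the design effect for newly diagnosed patients measured from randomisation (section 1.3.2), not a post-progression effect against external recurrent-GBM controls, so it should not be used here.

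The point is worth correcting before unblinding, but it concerns a secondary analysis without alpha and does not affect the primary endpoint.

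**What to change.** 1. In section 8.2.4, describe the comparison as pre- plus post-progression DCVax-L versus external controls, and remove the statement about priming.
2. For priming, add an exploratory Cox comparison of post-progression OS in DCVax-L-arm versus placebo-arm crossover patients, with a common time origin, adjusted for MGMT, age, KPS at crossover and time to progression. Show it also without time to progression, which is measured after randomisation and may itself reflect treatment.
3. Label it non-randomised: patients are selected on progression, on electing crossover and on remaining supply. State that differential vaccine-induced pseudo-progression can bias it.
4. Add a sensitivity analysis restricted to confirmed progression, or timed from the first crossover dose. If confirmed progression is used, confirm by imaging and start the clock at the confirming scan, because section 1.2.3 also counts death as confirmation and selecting on that would condition on the outcome.
5. Report crossover counts by arm and reconcile the two 90% statements.

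The cost is a wording change, one Cox model and its sensitivity analyses on data the trial already collects; protocol Appendix A1 schedules KPS at the first crossover visit. The downside is a wider interval, about HR × or ÷ 1.28 to 1.36 under the 90% crossover counts, and selection bias that adjustment will not fully remove.

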# 8.3 Statistical methods for the analysis of the secondary endpoints: comparisons internal to the DCVax®-L study

#### 8.3.1 Type I error

The secondary endpoints will be tested in the order shown in Table 2, Section 3, using a gatekeeping approach whereby an endpoint is tested for significance if its predecessor is significant at 2.409%.

#### 8.3.2 Analysis for OS, PFS

The intent of the original protocol was that the Cox proportional hazards model will be used for the primary analysis of OS. However the OS endpoint analysis may be confounded by non-proportional hazards due to the effects of the crossover option that was built into the protocol from the outset. Under this crossover option, all subjects from both arms of the Trial were allowed to opt to receive the active treatment DCVax®-L at the time of disease progression (measured by MRI), while remaining blinded to their initial treatment assignment. If subjects originally assigned to placebo receive treatment benefit in terms of extended survival as a result of this crossover option, then we can expect the survival curves to converge. To address possible non-proportionality while controlling type I error, a testing procedure based on a weighted log-rank statistic that was developed by Karrison will be used [28].

The intent of the original protocol was that the Cox proportional hazards model will be used for the primary analysis of PFS. When the protocol was developed in 2006 the phenomenon of pseudo-progression was largely unknown. Since then, pseudo-progression has become well recognised as a

major issue. It is now expected that, because early events specifically may not represent true disease progression, differentially in the two randomized groups, the proportional hazards assumption may not hold; the hazard ratio is expected to decrease with time as the effect of PsPD decreases.

For OS and PFS, Karrison's approach to the weighted log rank test will be used [28], based on the ITT population. A one-sided p value will be presented.

Along with the p value for the test, the hazard ratio, with a 95% confidence interval, will be presented. Estimates of 6, 12, 18, 24, 30, 36, 42, 48, 54 and 60 month OS and PFS will be provided, with 95% confidence intervals, for both randomized treatment groups.

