In the 15 years since TMZ was approved for GBM, scientific knowledge about GBM has advanced greatly. Today, many prognostic factors are well known (e.g., MGMT gene promoter status, IDH mutation status, age, extent of resection, performance status, etc.) and molecular sub-types of GBM have been identified and analyzed [3]. However, hundreds of clinical trials testing a wide range of diverse treatments have failed to achieve meaningful extension of survival. A survey of the trials conducted over more than a decade following TMZ approval (2005-2017) found that, out of 417 clinical trials involving 32,000 patients, there were only 16 Phase III randomized trials and only 1 of those trials was found to extend survival or provide other material benefit [4]. In the last 2 years, more Phase III clinical trials for GBM were reported, some including treatment with checkpoint inhibitor drugs (CPI), and all of these Phase III trials also failed to extend survival.

The only two new treatments approved for GBM in the 15 years since approval of TMZ in 2005 were both approved for commercial use with no extension of survival. The first is Bevacizumab, which received accelerated approval followed by full approval based on progression-free survival and improvement of quality of life, but no improvement in survival [5]. The second is the Optune tumor treating fields (TTF) device which was approved for recurrent GBM based upon non-inferiority with standard of care followed by a label extension to newly diagnosed GBM, based on prolongation of progression free survival and overall survival [6].

For all of the foregoing reasons, there is a severe unmet medical need for new and better treatments for GBM that extend survival. This Phase III trial of DCVax®-L, with an intent to treat (ITT) population of 331 patients, is one of the last remaining Phase III trials for GBM that is currently still active. To better analyze the data based on the current scientific advances and the recent understanding of the GBM biology, its natural history and response to therapy over the past 13 years, we have developed this SAP.

The design of this SAP has been developed by multiple independent experts, and reviewed by independent, leading neuro-oncology experts who were not involved in the Trial, and all of the analyses called for under this SAP will be carried out by independent experts. This SAP was developed prior to data lock and unblinding of the Trial data.

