#### 1.3 Sample size

#### 1.3.1 Sample size for PFS

The sample size calculations were based on PFS. Table 1 shows the assumptions made.

Table 1: Assumptions Made to Support Sample Size Calculation

Ratio between the treatment arm and the placebo arm	2:1
Accrual period	36 months
Time to accrual of 50% of subjects	22 months
Follow up period	5 months
Loss to follow up, per arm per month	1%
Median PFS for placebo arm	7 months
Test for comparing PFS between arms	Log rank
Type I error	$\alpha$ = 0.01, one sided

To achieve 84% power when median PFS is 11 months in DCVax®-L-treated subjects, 348 subjects would be required in total: 232 in the DCVax®-L arm and 116 in the placebo arm. The corresponding total number of events required is 248.

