#### 1.5 Randomization

Randomization was performed using an interactive web response system (IWRS) and was initiated upon a randomization request form submitted by the trial site followed by review of all eligibility criteria. The randomization was stratified by site and by MGMT methylation status (methylated/unmethylated), and used a permuted block design with a fixed block size.

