#### 8.3.3 Analysis for confirmed PFS

For confirmed PFS, the Cox proportional hazards model will be used.

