#### 1. OS, PFS and cPFS: Cox model (ITT)

A Cox proportional hazards regression model [29] based on the ITT population will be used. The following baseline covariates will be assessed (one at a time) for their additional contribution to the statistical model, and each covariate showing a significant (P < 0.05) contribution will be included in the final model, for each endpoint separately. Subjects with missing data in the continuous variables (age, KPS) will be excluded from the respective analysis. Hazard ratios, estimates of survival to 6, 12, 18, 24, 30, 36, 42, 48, 54 and 60 months and 95% confidence intervals will be provided.

- Sex: Male / female
- Age at randomization: years
- MGMT status at randomization: Yes, No, unknown
- Karnofsky Performance Status at randomization: score
- Extent of resection: Complete, partial (or incomplete), unknown
- Absolute lymphocyte count at randomization: ≤ 1,000 /μL, > 1,000/μL, unknown

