#### 8.4.2 Physical functioning

Physical functioning will be measured by the Karnofsky performance status (KPS). Both the score and the change from baseline will be summarized, and the change from baseline will be compared between the treatment groups and the controls groups using the Wilcoxon test stratified by MGMT methylation status. This analysis will be conducted for each visit separately.

The time from date of surgical resection to a 10-point decline in KPS will calculated. This endpoint will be analyzed using the Karrison approach as for the analysis of the secondary endpoints within study PFS and OS.

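### The alpha-carrying within-trial tests of cPFS, PFS and OS name no MGMT stratum although randomisation was stratified by MGMT; adding it is a modest, nearly free gain in power

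*Combined protocol and SAP*

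**What the plan says.** SAP Section 1.5 states: "The randomization was stratified by site and by MGMT methylation status", with two MGMT levels, methylated and unmethylated. The SAP introduction lists MGMT promoter status among the well-known prognostic factors. Section 1.2.1 (Analysis #3) names it first among the characteristics that define sub-groups with clearly different survival.

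The gatekept within-trial survival tests are these:

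- **PFS and OS (Section 8.3.2):** Karrison's "approach to the weighted log rank test will be used [28], based on the ITT population".
- **cPFS (Section 8.3.3):** "For confirmed PFS, the Cox proportional hazards model will be used".

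Neither section, nor Table 2, names a stratum or a covariate for them. Section 8.3.1 tests the secondary endpoints in Table 2 order, each only if the one before it is significant at 2.409%.

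MGMT appears in two other places among the within-trial survival analyses. In the exploratory Cox models of Section 8.3.4 it is a candidate assessed singly, and "each covariate showing a significant (P < 0.05) contribution will be included in the final model". In Section 8.3.5 it defines subgroups. By contrast, the exploratory comparison of KPS change is made "using the Wilcoxon test stratified by MGMT methylation status" (Section 8.4.2), and the immune-response logistic regression (Section 8.4.1) includes MGMT as a covariate.

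**The concern.** A factor worth stratifying the randomisation by is normally carried into the analysis. If it is strongly prognostic and left out, survival times within each arm are a mixture of two risk groups. The marginal hazard ratio then lies closer to 1 than the within-stratum ratio, and the test tends to reject less often than it could.

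Here the plan accounts for MGMT in some exploratory analyses but not in the randomised survival tests that carry alpha. Power matters in this family because the sequence is gated: a miss on cPFS closes PFS and OS. The primary endpoint and Secondary Endpoint #1 rest on external controls, so these tests are the formal randomised evidence on survival and progression.

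**Working it through.** **1. Reproduce the plan's own power (SAP Sections 1.3.1 and 1.3.2).** Schoenfeld's formula gives events d = (z_α + z_β)² / [p₁p₂(ln HR)²] and power = Φ(√(d·p₁p₂)·|ln HR| − z_α). The planned split is "232 in the DCVax®-L arm and 116 in the placebo arm", so p₁p₂ = (1/3)(2/3) = 0.2222.

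- **OS:** HR = 17/25.3 = 0.672, ln HR = −0.3976, one-sided α = 0.025. Events = (1.960 + 0.860)² / (0.2222 × 0.1581) = 226.3, so 227 (stated: 233). Power at 233 events = Φ(7.196 × 0.3976 − 1.960) = Φ(0.901) = 81.6% (stated: 80.5%).
- **PFS:** HR = 7/11 = 0.636, ln HR = −0.4520, one-sided α = 0.01. Events = (2.326 + 0.994)² / (0.2222 × 0.2043) = 243 (stated: 248). Power at 248 events = Φ(7.424 × 0.4520 − 2.326) = Φ(1.029) = 84.8% (stated: 84%).

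Both agree with the plan to within a few events and about one point of power.

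**2. Move to the trial as it stands.** The SAP introduction describes a trial "with an intent to treat (ITT) population of 331 patients". With 232 randomised to DCVax-L (Section 1.2.1), placebo is 331 − 232 = 99. At one-sided 2.409% and 232:99, the same formula gives 78.9% for OS and 90.0% for PFS.

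**3. Simulate with and without MGMT strata.** The inputs were:

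- 232:99 allocation, with MGMT balanced within arms;
- methylated share 199/(199 + 349) = 36%, taken from the external-control counts in Section 8.1.5 as a proxy;
- exponential survival, uniform accrual over 36 months, 1% loss per month;
- analysis at 233 deaths or 248 PFS events, one-sided 2.409%;
- 10,000 trials per scenario.

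The documents give no MGMT hazard ratio (methylated versus unmethylated), so it is varied as an assumption. There is no planning effect for cPFS, so PFS stands in for it. Each cell shows unstratified versus stratified log-rank, in percent.

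| Assumed MGMT HR | OS power | OS loss (points) | PFS power | PFS loss (points) | OS null rejection |
|---|---|---|---|---|---|
| 1.0 | 80.6 / 80.1 | none | 91.0 / 90.7 | none | 2.64 / 2.61 |
| 0.8 | 80.1 / 80.1 | 0 | 91.1 / 91.3 | 0 | 2.81 / 2.87 |
| 0.7 | 78.9 / 80.0 | 1 | 89.8 / 90.5 | 1 | 2.89 / 2.95 |
| 0.6 | 77.9 / 80.3 | 2 | 89.0 / 90.7 | 2 | 2.70 / 2.86 |
| 0.5 | 74.9 / 79.7 | 5 | 88.0 / 91.2 | 3 | 2.22 / 2.55 |
| 0.4 | 72.5 / 80.3 | 8 | 85.2 / 90.7 | 5 to 6 | 1.90 / 2.55 |

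Simulation error is about 0.4 points for each OS power figure.

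**4. Check the weighted test.** The documents do not give the details of Karrison's procedure. Taking the maximum of three weighted log-rank statistics as an assumed form, OS power is 75.9% versus 78.2% at MGMT HR 0.6, 72.3% versus 77.4% at 0.5, and 70.0% versus 78.4% at 0.4. The losses are about the same size.

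**5. Check with a separate simulation.** With the same allocation, methylated share, OS effect and alpha, it gave 76.6% versus 77.7% at MGMT HR 0.7, 76.0% versus 78.0% at 0.6, 73.9% versus 78.4% at 0.5 and 69.9% versus 77.7% at 0.4. The differences are 1.1, 2.0, 4.5 and 7.8 points, with no gain at 1.0.

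**The case against.** The strongest objection is that the gain is small, conditional and partly a matter of test size. With no MGMT hazard ratio in the documents, a weak MGMT effect means no gain. The last column of the table shows that the two tests do not reject equally often under the null, so raw power differences flatter stratification. In a variant with 60-month censoring and treatment HR 0.672, holding the stratified test to 2.409% cut the gain at MGMT HR 0.5 from 3.8 to about 2.4 points. Over the treatment effects tried in that variant, it left 1 to 2 points at MGMT HR 0.6 and about zero at 0.7. This stands as a limit on the size. It is not a reason against stratifying: with no MGMT effect, both tests rejected 2.7% in 60,000 null runs, so the slight excess over 2.409% comes from the one-sided log-rank approximation at 2:1 allocation and not from the strata.

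The absolute power figures are also not the trial's. The SAP itself expects crossover to blur OS and pseudo-progression to confound PFS, and neither is simulated. Nor is an unknown-MGMT stratum. In the two external studies with MGMT curves (Table 3), 640 − 548 = 92 of 640 controls (14%) fall in neither curve, so the handling of unknown status could matter.

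A reader might infer four stronger things that the documents do not support:

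- **That the tests are invalid.** The omission does not inflate type I error. The pull of the marginal hazard ratio towards 1 reflects non-collapsibility, not confounding.
- **That the SAP chose an unstratified analysis.** It is silent. As written there is no MGMT term, but the SAP does not say that strata are excluded.
- **That MGMT is ignored throughout.** It appears in the exploratory Cox models, the subgroups, the KPS test and the immune-response model.
- **That these are the only randomised comparisons.** Tumour response, TTP, KPS and immune response also compare randomised arms, and the pseudo-progression cohort was randomised too.

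Whether the P < 0.05 screening in the exploratory Cox models should be replaced is a separate question and not part of this point.

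**Conclusion.** The point holds as a free improvement. The gatekept tests of cPFS, PFS and OS name no term for a factor that the trial stratified by and that the SAP calls prognostic. At the planning effects, the cost is zero to about 8 points of power for OS and zero to about 6 for PFS as the assumed MGMT hazard ratio goes from 1.0 to 0.4; at 0.6 it is about 2 points for each. Part of that is the unstratified test's lower null rejection rate. The figures assume proportional hazards, 36% methylated, two known MGMT levels, and no crossover or pseudo-progression effect. For cPFS they are borrowed from PFS. The gain is modest, and the tests as written remain valid.

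**What to change.** Before unblinding, amend SAP Sections 8.3.2 and 8.3.3 and Table 2 to state that the Cox model for cPFS and the weighted log-rank tests of PFS and OS are stratified by the MGMT status used at randomisation. For the weighted test, sum the scores and their covariances over strata.

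Add a rule for unknown status: Section 8.3.4 lists an unknown level, while Section 1.5 lists only two.

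State that site is left out of the strata. With approximately 90 sites (protocol Section 3.4), 331/90 is fewer than 4 patients per site, even before splitting by MGMT.

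The cost is a few sentences of SAP text and minor programming to stratify the weighted test. MGMT status has already been collected, and the SAP states that it precedes data lock and unblinding.
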